8.1.2. Calculation of the Summary Statistics

For continuous data the following rules will be applied:

- Missing values will not be imputed, unless specifically stated otherwise.
- Unrounded data will be used in the calculation of summary statistics.

- If the number of subjects with valid observations (n) <3, summary statistics will not be calculated, with the exception of n, minimum, and maximum.
- In general, as early termination data are not associated with any scheduled timepoint, they will be excluded from all calculations of summary statistics and statistical analyses. Exceptions may be made where justified.

For categorical data the following rules will be applied:

- For ordered categorical data (eg, AE severity), all categories between the possible minimum and maximum categories will be included, even if n = 0 for a given category.
- For non-ordered categorical data (eg, race), only those categories for which there is at least 1 subject represented will be included; unless specifically stated otherwise.
- Missing values will not be imputed, unless specifically stated otherwise. A ‘missing’ category will be included for any parameter for which information is missing. This will ensure that the population size totals are consistent across different parameters.

8.1.3. Repeat and Unscheduled Readings

For vital signs and 12-lead ECG data only, any predose value recorded in addition to the original value or a postdose value recorded within 15 minutes of the original value will be defined as a repeat value; any postdose value recorded more than 15 minutes after the original value will be defined as an unscheduled value. For all other data types (eg, laboratory parameters), any value recorded in addition to the original value will be defined as an unscheduled value.

The original value will be replaced by the last associated repeat value in all calculations, with the exception of the 12-lead ECG outlier analysis (see [Section 8.7.4](#)).

As unscheduled values are not associated with any scheduled timepoint, they will be excluded from all calculations, with the exception of the baseline derivation (see [Section 8.1.4](#)) and 12-lead ECG outlier analysis (see [Section 8.7.4](#)).

8.1.4. Definitions of Baseline, Change from Baseline, Percent Change from Baseline and Fold Change from Baseline

The baseline will be defined as the value recorded prior to dosing. If the date/time of the value is incomplete or missing, it will be excluded from the baseline calculation, unless the incomplete date/time indicates the value was recorded prior to dosing.

Individual changes from baseline will be calculated by subtracting the individual subject’s baseline value from the value at the postdose timepoint.

Fold Change from baseline = (Final Value / Baseline Value);

The summary statistics for change from baseline and fold changes from baseline will be derived from individual subjects’ values (eg, mean change from baseline will be the mean of

the individual changes from baseline for all subjects, rather than difference between the mean value at the postdose timepoint and mean value at baseline).

See [Section 8.1.3](#) for more detail on handling repeat and unscheduled readings in the calculations.

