7.3. Anti-AMG 592 and Anti-IL-2 Assessments

Blood samples for antibody testing are to be collected at the times listed in the Schedule of Assessments ([Appendix 8](#)). Samples testing positive for anti-AMG 592 and/or anti-IL-2 antibodies will also be tested for neutralizing antibodies and may be further characterized. More frequent testing or testing for a longer period of time may be required in the event of a safety-related concern.

Subjects who test positive at the EOS timepoint for neutralizing antibodies to IL-2 or binding antibodies with potentially antibody-mediated clinical sequelae will be asked to return for follow-up testing. This testing is to occur approximately every 3 months starting from the EOS visit and continue until: 1) antibodies are no longer detectable or 2) the subject has been followed for a period of at least 12 months (\pm 4 weeks) post administration of AMG 592 (whichever is shorter). All follow-up results, both positive and negative, will be communicated to the study site.

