8.5. Anti-AMG 592 and Anti-IL-2 Analyses

The formation of anti-AMG 592 and anti-IL-2 antibodies will be summarized descriptively. The incidence and percentage of subjects who develop antidrug antibodies (binding and if positive, neutralizing) at any time will be tabulated by treatment group.

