1. INTRODUCTION

This SAP is to provide details of statistical analysis that have been outlined within the clinical study protocol for study 20200102 (Final Version dated 01 April 2021, Amendment 1 dated 08 December 2021, Amendment 2 dated 28 April 2022) and electronic case report form (eCRF).

This SAP describes the planned analysis of the pharmacokinetic (PK), pharmacodynamic (PD), safety, and tolerability data from this study. A detailed description of the planned TFLs to be presented in the clinical study report (CSR) is provided in the accompanying TFL shells document.

In general, the analyses are based on information from the protocol, unless they have been modified by agreement with Amgen Inc. A limited amount of information about this study (eg, objectives, study design) is given to help the reader's interpretation.

This SAP must be finalized prior to the lock of the clinical database. Additionally, the SAP and TFL shells should be finalized prior to any programming activities commencing.

This SAP supersedes any statistical considerations identified in the protocol; where considerations are substantially different, they will be so identified. If additional analyses are required to supplement the planned analyses described in this SAP, they may be performed and will be identified accordingly in the CSR. Any substantial deviations from this SAP will be agreed with Amgen Inc. and identified in the CSR.

This SAP is written with consideration of the recommendations outlined in the International Conference on Harmonisation (ICH) E3 guideline *Structure and Content of Clinical Study Reports*, ICH E8 guideline *General Considerations for Clinical Trials*, ICH E9 guideline *Statistical Principles for Clinical Trials*.^{1,2,3}

The document history is presented in Appendix 1.

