8. STATISTICAL METHODOLOGY

8.1. General

Listings will be provided for all data captured in the database, including medical history. Listings will include all subjects assigned to the all subjects population and include data up to the point of study completion or discontinuation. Subjects are generally considered to have completed the study if they complete the scheduled end of study visit (rather than early termination visit). Any subject who discontinues the study will be identified accordingly in the listings. Summaries and statistical analyses will include the subjects assigned to the relevant population based on data type.

Data analysis will be performed using the SAS® statistical software package Version 9.4 (or higher if a new version is issued during the study).

Analysis Data Model (ADaM) datasets will be prepared using Clinical Data Interchange Standards Consortium (CDISC) ADaM Version 2.1 (or higher if a new version is issued during the study) and CDISC ADaM Implementation Guide Version 1.1 (or higher if a new version is issued during the study). Pinnacle 21 Community (version 3.1.2 or higher) will be utilized to ensure compliance with CDISC standards.

Caution should be used when interpreting results from the statistical analyses conducted in this study because the sample size is not based on power calculations.

Where reference is made to 'valid' data, this refers to non-missing data which meet the predetermined criteria (eg, are not flagged for exclusion).

Where reference is made to 'all calculations', this includes, but is not limited to, summary statistics, statistical analyses, baseline derivation, changes from baseline, percentage changes from baseline, and any parameter derivations.

All figures will be produced on linear-linear or discrete-linear scales, as applicable, unless specifically stated otherwise.

8.1.1. Handling of Data Quality Issues Due to Coronavirus Disease 2019 and Related Restrictions

Due to COVID-19 and related restrictions, there is a high risk for impact to data integrity, with the recognized potential for:

- Missed visits, caused by, for example:
 - Subject unable to travel to site due to restrictions, the need to quarantine, or COVID-19 infection
 - Subject unwilling to go to site due to fear of COVID-19 infection
 - Site postponing subject's visit due to investigator not being available (eg, if they have been dispatched to hospital handling COVID-19 infections)

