8.7.5. Antibodies

The formation of anti-AMG 592 and anti-IL-2 antibodies will be summarized descriptively. The incidence and percentage of subjects who develop anti-AMG 592 antibodies and cross reactive anti-IL-2 antibodies (binding and if positive, neutralizing) will be summarized by treatment group. Furthermore, the incidence and percentage of subjects with treatment boosted anti-AMG 592 antibodies will also be summarized. In addition, subjects with positive binding and neutralizing anti-AMG 592 results will be listed individually with corresponding time points.

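### SAP 8.1.3, on its most natural literal reading, drops unscheduled antibody results from the incidence summary, although Protocol 8.5 counts antibodies that develop at any time (low materiality)

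*SAP*

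**What the plan says.** **The general rule.** Outside vital signs and ECG data, SAP section 8.1.3 defines an unscheduled value as follows: "For all other data types (eg, laboratory parameters), any value recorded in addition to the original value will be defined as an unscheduled value". It then states: "As unscheduled values are not associated with any scheduled timepoint, they will be excluded from all calculations, with the exception of the baseline derivation". One further exception follows, the 12-lead ECG outlier analysis. SAP section 8.1 explains what all calculations means: "this includes, but is not limited to, summary statistics, statistical analyses, baseline derivation, changes from baseline".

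**The antibody analysis.** SAP section 8.7.5 states: "The incidence and percentage of subjects who develop anti-AMG 592 antibodies and cross reactive anti-IL-2 antibodies (binding and if positive, neutralizing) will be summarized". It adds a summary of treatment-boosted anti-AMG 592 antibodies and a listing: "In addition, subjects with positive binding and neutralizing anti-AMG 592 results will be listed individually with corresponding time points". It says nothing about unscheduled samples.

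**The protocol.** Section 8.5 states: "The incidence and percentage of subjects who develop antidrug antibodies (binding and if positive, neutralizing) at any time will be tabulated by treatment group". Section 7.3 provides for further sampling: "More frequent testing or testing for a longer period of time may be required in the event of a safety-related concern".

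**Which document governs.** SAP section 1 states: "This SAP supersedes any statistical considerations identified in the protocol; where considerations are substantially different, they will be so identified". SAP section 10 reports no significant change from the protocol-specified analyses.

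**The concern.** Antibody incidence is a secondary objective. The protocol's count looks across all time after dosing. The SAP's general rule removes results that belong to no scheduled timepoint, and the SAP's antibody section neither repeats *at any time* nor claims an exception.

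The samples at risk are the ones that Protocol 7.3 would add because of a safety concern. A positive result on such a sample would appear in the listing while the incidence table of the same report counted the subject as negative. The error can go only one way. Removing postdose results can turn a subject who developed antibodies into an apparent negative, but never the reverse.

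**Working it through.** The plan states no antibody rate, so there is no figure to reproduce. The check sets the passages side by side and then sizes the effect.

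**Step 1: does the rule reach antibody results?**

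- Antibody results are neither vital signs nor ECG data, so the definition for all other data types applies.
- Values that meet it are left out of all calculations, a term that SAP 8.1 says includes summary statistics. An incidence and percentage is a summary statistic.
- Neither exception (baseline derivation, ECG outlier analysis) covers antibody incidence, and SAP 8.7.5 adds none.

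**Step 2: which samples are left?** Protocol Appendix 3 allows four antibody samples per subject. The schedule in Appendix 8 places one before dosing and three after. Under the literal rule, three scheduled postdose results decide whether a subject counts. Under Protocol 8.5, any postdose result can.

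**Step 3: size.** SAP section 4 gives 8 subjects in each of 4 groups, and 4 × 8 = 32 agrees with its total. If one subject is positive only on an unscheduled sample, the rate falls by 1/n:

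- one group: 1/8 = 12.5 points
- all subjects: 1/32 = 3.1 points
- the Overall column in SAP section 6, if it pools three groups: 1/24 = 4.2 points. This is an assumption, because the doses are redacted.

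For scale, these are exact (Clopper-Pearson) 95% limits. The lower limit is the 0.025 quantile of Beta(x, n−x+1) and the upper is the 0.975 quantile of Beta(x+1, n−x). For x = 0 the lower limit is 0 and the upper is 1 − 0.025^(1/n).

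| Situation | Literal SAP rule | Protocol rule |
|---|---|---|
| Group of 8, no other positive | 0/8 = 0% (0 to 36.9%) | 1/8 = 12.5% (0.3 to 52.7%) |
| Group of 8, one positive on a scheduled sample | 1/8 = 12.5% (0.3 to 52.7%) | 2/8 = 25.0% (3.2 to 65.1%) |
| All 32, no other positive | 0/32 = 0% (0 to 10.9%) | 1/32 = 3.1% (0.1 to 16.2%) |

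The counts are illustrations, and the plan calls for no such intervals. They show that one subject moves a group's rate visibly, but by far less than the uncertainty already present at n = 8.

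**The case against.** **The definition may be narrower.** An additional value presupposes an original one. A sample from an extra visit has no original beside it, so one can argue that it falls outside the definition and is never excluded. This reading is possible. But the reason that 8.1.3 gives, the lack of a scheduled timepoint, fits an extra-visit sample better than a retest at a planned visit. The literal exclusion therefore remains the more natural reading, though not the only one.

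**The exceptions may be boilerplate.** SAP 8.1.3 exempts an ECG outlier analysis, yet SAP 8.7.4 describes only listing and flagging. The section may not have been tailored to this study, so its silence on antibodies is weak evidence of intent. This stands as a point about intent. It does not give a programmer a rule to follow instead.

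**The documents can be read in harmony.** SAP 8.7.5 counts subjects, not visits. The SAP promises to identify substantial differences from the protocol and identifies none. The authors may have meant the rule only for by-timepoint tables, and the table shells, which are not available here, may settle it. All of this is fair. Yet an undeclared departure is still a departure if the text is followed, and the SAP says that it supersedes the protocol on statistics.

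**Early termination and follow-up.** A reader might infer that early-termination antibody results are lost as well. The exclusion of early-termination data in SAP 8.1.2 sits under continuous data and sets no rule for antibody status. A reader might also infer that follow-up after the end-of-study visit could reveal new antibody-positive subjects whom the table misses. Protocol 7.3 limits the three-monthly follow-up to subjects already antibody-positive at that visit. At most, it could change a neutralizing result.

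**Conclusion.** The concern holds as a conditional wording defect. On its most natural literal reading, SAP 8.1.3 takes unscheduled antibody results out of the incidence summary in 8.7.5. That departs from Protocol 8.5 without being declared. It can only understate developed-antibody incidence, by 12.5 percentage points per affected subject in a group of 8. The effect is zero unless some subject's only positive result is on an unscheduled sample.

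A reader might go further and infer that the reported incidence will be wrong, or that positive results will disappear. The documents do not support either. They record no extra antibody sample. SAP 8.7.5 lists anti-AMG 592 positives individually, and SAP 8.1 lists all captured data up to study completion or discontinuation. The individual listing does not name anti-IL-2 results, so a result positive only for those would have to be found in the general listings.

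Materiality is low, because the endpoint is secondary and descriptive and no inferential analysis is planned. The sizing assumes the planned group sizes. Confidence in the literal reading is moderate, given the narrower reading of the definition and the unseen table shells.

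**What to change.** Restore *at any time* in SAP 8.7.5 and add antibody incidence to the exceptions in 8.1.3. Suggested sentence for 8.7.5:

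*Subjects who develop antibodies (binding and, if positive, neutralizing) at any time after dosing are counted, using all postdose samples, scheduled or unscheduled; subjects positive before dosing are not counted as developing antibodies and are assessed for the treatment-boosted summary.*

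The second clause matters. A rule that simply counted any positive postdose sample would sweep in subjects already positive before dosing. Both documents count subjects who develop antibodies, and SAP 8.7.5 summarises boosted antibodies separately.

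Follow-up after the end-of-study visit needs mention only for neutralizing status. Leave 8.1.3 unchanged for by-timepoint tables. If the exclusion is intended, declare it in SAP section 10 as a change from the protocol.

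The cost is one sentence and a short exception, with no new data and no new table. The downside is small: subjects sampled more often have more chances to test positive. The individual listing shows the timepoint of each positive anti-AMG 592 result, so a reader can see where that has happened.

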8.2. Subject Disposition and Population Assignment

Subject disposition and population assignment will be listed.

A summary table by treatment groups will be provided, based on the safety population.

8.3. Screening Demographics and Baseline Characteristics

The screening demographics and baseline characteristics including age, sex, race, ethnicity, height, body weight, and body mass index will be listed.

A summary table by treatment groups will be provided, based on the safety population.

8.4. Prior and Concomitant Medication

Prior medication will be defined as medication that ends prior to dosing. Concomitant medication will be defined as medication that starts during or after dosing or starts but does not end prior to dosing.

Prior and concomitant medications will be coded using the World Health Organization Drug Dictionary (WHODrug) Global, Format B3, Version September 2020 (or later if a new version is issued during the study; see the data management plan [DMP] for more details). Prior and concomitant medications will be listed.

8.5. Pharmacokinetic Assessments

8.5.1. Pharmacokinetic Analysis

The following PK parameters will be determined where possible from the serum concentrations of AMG 592 using noncompartmental methods in validated software program Phoenix WinNonlin (Certara, Version 8.1 or higher):

Parameter	Units ^a	Definition
AUC _{last}	hr*ng/mL	area under the concentration-time curve from time zero to time of last quantifiable concentration ^b
AUC _{inf}	hr*ng/mL	area under the concentration-time curve from time zero extrapolated to infinity ^c
%AUC _{extrap}	%	percentage of area under the concentration-time curve due to extrapolation from the last quantifiable concentration to infinity
C _{max}	ng/mL	maximum observed concentration
CL/F	L/hr	apparent total body clearance, calculated as Dose/AUC _{inf}
MRT _{inf}	hr	mean residence time observed from time zero to infinity

Vz/F	L	apparent volume of distribution based on the terminal phase, calculated as Dose/(AUC _{inf} *λ _z)
t _{max}	hr	time of maximum observed concentration
t _{last}	hr	time of the last quantifiable concentration
t _{1/2}	hr	apparent terminal elimination half-life

^a Units are based on concentration units (provided by the bioanalytical lab or preferred units for presentation of PK parameters) and dose units used in the study.

^b The area under the concentration-time curve will be calculated using the linear trapezoidal linear interpolation rule.

^c Based on the last observed quantifiable concentration

Additional PK parameters may be determined where appropriate.

Pharmacokinetic analysis will be carried out where possible using actual dose administered (μg) and actual postdose blood sampling times. If an actual time is missing, the sample concentration result will be treated as missing unless there is scientific justification to include the result using the nominal time.

The parameters C_{max}, t_{last}, and t_{max} will be obtained directly from the concentration-time profiles. If C_{max} occurs at more than 1 timepoint, t_{max} will be assigned to the first occurrence of C_{max}.

8.5.1.1. Criteria for the Calculation of Apparent Terminal Elimination Rate Constant and Half-life

The start of the terminal elimination phase for each subject will be defined by visual inspection and generally will be the first point at which there is no systematic deviation from the log-linear decline in concentrations.

The apparent terminal elimination rate constant (λ_z) will only be calculated when a reliable estimate can be obtained using at least 3 data points, preferably not including C_{max}, and the adjusted coefficient for determination of exponential fit (R²-adj) of the regression line is ≥0.8. Parameters requiring λ_z for their calculation (eg, AUC_{inf} and t_{1/2}) will only be calculated if the R²-adj value of the regression line is ≥0.8.

The following regression-related diagnostic PK parameters will be determined, when possible:

Parameter	Units	Definition
λ _z	1/h	apparent terminal elimination rate constant
λ _z Upper	hr	end of exponential fit
λ _z Lower	hr	start of exponential fit
λ _z N	NA	number of data points included in the log-linear regression
λ _z Span Ratio	NA	time period over which λ _z was determined as a ratio of t _{1/2}
R ² -adj	NA	adjusted coefficient for determination of exponential fit

Where possible, the span of time used in the determination of λ_z (ie, the difference between λ_z Upper and λ_z Lower) should be ≥ 2 half-lives. If the λ_z Span Ratio is < 2 , the robustness of the $t_{1/2}$ values will be discussed in the clinical study report (CSR).

8.5.1.2. Criteria for Calculation and Reporting of Area Under the Concentration-time Curve

The minimum requirement for the calculation of AUC will be the inclusion of at least 3 consecutive concentrations above the lower limit of quantification. If there are only 3 consecutive concentrations, at least 1 should follow C_{max} .

If the extrapolated area is $> 20\%$, AUC_{inf} (and derived parameters, CL/F and Vz/F) will be excluded from the summary statistics.

8.5.1.3. Criteria for Handling Below the Limit of Quantification or Missing Concentrations for Pharmacokinetic Analysis

Serum concentrations below the limit of quantification (BLQ) will be assigned a value of 0 before the first measurable concentration and thereafter BLQ concentrations will be treated as missing. The following rules apply to the specific situations defined below:

- If an entire concentration-time profile is BLQ, it will be excluded from PK parameter analysis.
- Where 2 or more consecutive concentrations are BLQ at the end of a profile, the profile will be deemed to have terminated and any further quantifiable concentrations will be set to missing for the calculation of the PK parameters, unless they are considered to be a true characteristic of the profile of the drug.
- If a predose serum concentration is missing, it will be set to 0 by default within Phoenix WinNonlin.

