1.2. Pharmacokinetics

In a first-in-human (FIH) study (Study 20140324), PK results of AMG 592 in healthy subjects following single-dose subcutaneous (SC) administration of AMG 592 are available for doses of CCI [REDACTED]. Results show dose-related increases in AMG 592 serum exposure (as assessed by maximum observed concentration [C_{max}] and area under the serum concentration-time curve [AUC] from time zero to infinity [AUC_{inf}]) with approximately dose-proportional increase over the CCI [REDACTED] CCI [REDACTED]. Following SC administration, the median time to maximum observed serum concentration (t_{max}) ranged from approximately 0.5 to 1 day with terminal phase half-life ($t_{1/2}$) about 11 to 13 hours postdose at doses [REDACTED].

In a single-dose PK study in healthy Japanese subjects (Study 20180132), exposure of AMG 592, assessed by C_{max} and AUC_{inf} , increased approximately dose proportionally over the CCI [REDACTED]. Mean C_{max} and AUC_{inf} exhibited CCI [REDACTED]. The median t_{max} was 14 hours in the AMG 592 CCI [REDACTED] cohort and 24 hours in the AMG 592 CCI [REDACTED] cohort. For the CCI [REDACTED] cohort, the mean half-life, apparent drug clearance, volume of distribution, and mean residence time was 11.7 hours, 1.29 L/hour, 21.9 L, and 33.2 hours, respectively. For the CCI [REDACTED] cohort, the mean half-life, apparent drug clearance, volume of distribution, and mean residence time was 9.68 hours, 0.852 L/hour, 11.7 L, and 39.5 hours, respectively.

In a multiple-dose study in patients with active rheumatoid arthritis (RA), exposure to AMG 592, as expressed in AUC and C_{max} , increased with increasing dose from CCI [REDACTED] every 2 weeks (Q2W) to CCI [REDACTED] once weekly (QW) to CCI [REDACTED] Q2W. Peak concentrations were observed about 6 to 12 hours following dosing, with half-lives that ranged from about 10 to 40 hours. Moderate drug accumulation was observed for

CCI Q2W and CCI QW. There were not enough data to determine the accumulation ratio for the CCI Q2W dose.

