8.3. Pharmacokinetic Analyses

The serum PK parameters of AMG 592 will be calculated using standard noncompartmental methods.

The primary PK parameters are C_{max} , t_{max} , AUC_{last} , and AUC_{inf} for AMG 592. All other PK parameters will be regarded as secondary and will not be subject to inferential statistical analysis.

Additional PK parameters may be calculated. Specific details will be presented in the Statistical Analysis Plan for this study.

CCI [REDACTED]

[REDACTED]

[REDACTED]

[REDACTED]

[REDACTED]

[REDACTED]

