8.5.2. Presentation of Pharmacokinetic Data

If the actual time of sample collection deviates from the nominal time by more than $\pm 10\%$, the serum concentration will be flagged.

For serum concentration data the following rules will apply:

- Values that are BLQ will be set to 0 for the calculation of summary statistics.
- Arithmetic mean or median values that are BLQ will be presented as 0.

For PK parameters the following rule will apply:

Geometric mean and coefficient of variation will not be calculated for t_{last} or t_{max} .

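### The 20% extrapolation rule in SAP 8.5.1.2 removes AUCinf, CL/F and Vz/F from the summaries but does not name MRTinf, which rests on the same extrapolation

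*SAP*

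**What the plan says.** The parameter table in SAP 8.5.1 includes MRTinf, defined as "mean residence time observed from time zero to infinity". The same table gives CL/F as "apparent total body clearance, calculated as Dose/AUC", with AUCinf as the denominator, but gives no formula for MRTinf.

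The exclusion rule is in SAP 8.5.1.2. It opens with "If the extrapolated area is", sets the limit at more than 20%, and on the parameters that depend on AUCinf says "and derived parameters, CL/F and Vz/F) will be excluded from the summary statistics". The list has two members and is not marked as giving examples. SAP 8.5.1.1, by contrast, does mark its list of parameters that need λz as examples.

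Two other rules could bear on MRTinf:

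- **SAP 8.5.1.1.** λz needs at least three points, preferably without Cmax. Parameters that depend on it "will only be calculated if the R²-adj value of the regression line is ≥0.8". This tests the fit of the regression, not the size of the extrapolated area.
- **SAP 8.5.2.** "Geometric mean and coefficient of variation will not be calculated for" tlast or tmax. MRTinf is not mentioned.

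On status, Protocol 8.3 names Cmax, tmax, AUClast and AUCinf as primary and says "All other PK parameters will be regarded as secondary and will not be subject to inferential statistical analysis".

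**The concern.** A rule that removes an unreliable AUCinf should also remove what is computed from it. The SAP does this for CL/F and Vz/F but not for MRTinf. Followed literally, a subject with more than 20% extrapolation loses the first three values and keeps the fourth.

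Two things are at stake, both modest. The MRTinf summary could include values that the plan's own standard would call unreliable. And CL/F and MRTinf in the same table could be summarised on different subjects. MRT is among the figures that Protocol 1.2 reports for each cohort of the earlier Japanese study (for one cohort, half-life, clearance, volume and "mean residence time was 11.7 hours, 1.29 L/hour, 21.9 L, and 33.2 hours"), so a reader may well set the new values beside those.

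**Working it through.** **Inputs from the documents.** The 20% limit (SAP 8.5.1.2). Half-life, CL/F, volume and MRT of two earlier cohorts (Protocol 1.2): A = 11.7 h, 1.29 L/h, 21.9 L, 33.2 h; B = 9.68 h, 0.852 L/h, 11.7 L, 39.5 h. Sampling at 6, 12, 16, 24, 48 and 72 h and later (Protocol Appendix 8).

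**Assumed.** MRTinf = AUMCinf/AUCinf, and the profile shapes in step 3.

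**1. Do the protocol's figures fit together?** The plan states no figure for this rule, so its prior PK was checked. Volume = (CL/F) × half-life / ln 2. Cohort A: 1.29 × 11.7 / 0.693 = 21.8 L (stated 21.9). Cohort B: 0.852 × 9.68 / 0.693 = 11.9 L (stated 11.7). Both agree within 2%.

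**2. Extrapolated share of AUMC.** The AUC tail is Clast/λz. The AUMC tail is Clast·tlast/λz + Clast/λz². Their ratio, tlast + 1/λz, is the mean time of the tail. With f the extrapolated share of AUC,

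AUMC share = f × (tlast + 1/λz) / MRTinf.

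The observed part lies wholly before tlast, so MRTinf is below tlast + 1/λz. The AUMC share therefore exceeds f for any profile.

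**3. Size at f = 20%.** Three absorption profiles were used. Two are chains of equal first-order steps tuned to the half-life and MRT of cohorts A (2 steps) and B (4 steps). For A, 1/λz = 11.7/0.693 = 16.9 h, and 16.9 + 2/0.1225 = 33.2 h. The third is a single first-order absorption with the 11.7 h half-life and an assumed rate of 0.1/h. MRTinf in the table comes from numerical integration to tlast plus a single-exponential tail from Clast, so it lies slightly below each profile's own MRT.

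| Profile | tlast (h) | 1/λz (h) | MRTinf (h) | AUMC share |
|---|---|---|---|---|
| A type | 45.8 | 16.9 | 32.2 | 0.2 × 62.7/32.2 = 39% |
| B type | 50.6 | 14.0 | 37.9 | 0.2 × 64.6/37.9 = 34% |
| First-order | 38.8 | 16.9 | 26.1 | 0.2 × 55.7/26.1 = 43% |

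**4. λz underestimated by 20%, same cut-off.** AUCinf ratio = 0.8 + 0.2/0.8 = 1.05, so the CL/F ratio is 1/1.05 = 0.952 (-4.8%). The Vz/F ratio is 1/(1.05 × 0.8) = 1.190 (+19.0%). Write a = f·tlast/MRTinf and b = f/(λz·MRTinf). The MRTinf ratio is [(1 - a - b) + a/0.8 + b/0.64] / 1.05.

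- A type (a = 0.284, b = 0.105): (0.611 + 0.355 + 0.164)/1.05 = 1.076, or +7.6%.
- B type (a = 0.267, b = 0.074): (0.659 + 0.334 + 0.115)/1.05 = 1.055, or +5.5%.
- First-order (a = 0.298, b = 0.130): (0.573 + 0.372 + 0.202)/1.05 = 1.093, or +9.3%.

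**5. When would the rule apply?** AUC extrapolation on the planned schedule, by last quantifiable sample:

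| Last sample | A type | B type | First-order |
|---|---|---|---|
| 48 h | 18.1% | 24.6% | 12.4% |
| 72 h | 4.9% | 6.0% | 3.2% |

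The limit is reached mainly by profiles that end at or before about 48 h.

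**6. Effect on a group mean.** About 32 subjects in four groups is 32/4 = 8 per group. One retained value that is 5.5% to 9.3% too high, in a subject otherwise at the group average, moves the arithmetic mean by 5.5/8 = 0.7% to 9.3/8 = 1.2%.

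**The case against.** The strongest reply is that few such values would exist. MRTinf needs λz. With Cmax observed at 16 h or 24 h, a profile ending at 48 h has only two or one later points, so the three-point criterion is not met unless Cmax is included in the fit. This stands as a limit on frequency. It does not close the gap: the SAP only prefers to leave Cmax out, a peak at 12 h or earlier leaves three later points, and R²-adj does not measure extrapolation.

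It can also be said that %AUCextrap is a planned parameter, so an affected subject can be identified. That is true, but it does not take the value out of the summary. Nor are the table shells available, so retention of MRTinf is inferred from the absence of any rule removing it.

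Four stronger readings are tempting, and the documents do not support them:

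- **An error near +14%.** A mono-exponential profile gives 52% of AUMC extrapolated and +14% in MRTinf for the same λz error. But with an 11.7 h half-life its MRT would be 11.7/0.693 = 16.9 h, against 33.2 h in Protocol 1.2, and it would peak at time zero, whereas that study's median tmax values were 14 h and 24 h.
- **MRTinf is always more sensitive than CL/F.** Only the larger extrapolated share is general. For the B-type profile the proportional sensitivity to λz is 0.21 against 0.20 at 20% extrapolation, and it reverses at 30% (0.28 against 0.30) and 40% (0.33 against 0.40). Vz/F, which the rule already covers, is more sensitive than MRTinf at the cut-off.
- **The distortion falls on Group 1.** Lower concentrations could fall below quantification sooner, but doses are blacked out and no quantification limit is given.
- **Ethnic comparisons would be biased.** No comparison of MRT between groups is planned, and the Caucasian comparator is at the high dose.

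**Conclusion.** The omission is real and minor. SAP 8.5.1.2 leaves MRTinf out of a rule whose reasoning applies to it. At the cut-off about 34% to 43% of AUMC is already extrapolated, and a 20% underestimate of λz shifts MRTinf by roughly +5% to +10% against about -5% for CL/F. MRTinf is therefore at least about as sensitive there as a parameter that the plan excludes.

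No primary endpoint is touched and no inference is planned. The sizes rest on the standard definition of MRTinf and on assumed absorption shapes with λz at the true terminal rate; the first-order profile matches the earlier half-life but not the earlier MRT. How many subjects are affected, and in which group, cannot be determined from the documents.

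**What to change.** In SAP 8.5.1.2, extend the bracketed list of derived parameters so that it names CL/F, Vz/F and MRTinf. If there is a reason to keep MRTinf in the summaries, state it and flag the values that come from profiles above 20% extrapolation.

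The cost is one exclusion flag in the PK parameter dataset and possibly a few fewer MRTinf values summarised. No new analysis is needed. Making the change before database lock avoids deciding on exclusions after the values have been seen.
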